There is currently limited information regarding the role of blood management in the benign gynecologic population and specifically, in patients who are scheduled to undergo surgery for fibroids and/or abnormal uterine bleeding. A thorough search through PubMed and clinicaltrials.gov did not reveal any studies on this issue. In 2019 at CCF only 2% of gyn patients at Main Campus were referred to blood management, but 12.6% of the main campus gyn population had a Hb of <10.0 g/dL. The overall goal of this study is to evaluate the role of preoperative blood management in optimizing surgical outcomes by reducing the co-morbidities associated with postoperative blood transfusion.

Specific Aims/Objective:

The primary objective of this study is to compare the change in baseline hemoglobin levels in patients in the study (Blood Management Protocol) and control ("usual care")

group who are undergoing hysterectomy for abnormal uterine bleeding. Change in baseline hemoglobin levels is defined as the difference of the hemoglobin level obtained within 72 hours prior to surgery and the hemoglobin level at 4 weeks postoperatively.

Our secondary objectives include 1. To evaluate the perioperative outcomes between the two groups including OR times, EBL, peri-operative transfusion rates, length of hospital stay, complications including intra-operative injuries, postoperative infection rates, readmission, and re-operation; 2. to assess patient satisfaction regarding their experience with the Blood Management protocol and extra outpatient infusion visits required using a patient questionnaire (PATSAT 35, Attached); and 3. to compare the quality of patient health and recovery between the two groups using the RAND-36 (Attached) assessment tool. The REDCap database will include potential identifiers to enable online surveys. The included potential patient identifiers include: date of birth, surgery date, and subject email (they provide for the study.)

Data variables that will be collected in the study are visible in the following table.

Patier	nt Demographics:
•	MRN
•	Age/ Date of Birth
•	BMI

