The intervention will include pre-surgical optimization blood management referral based on preoperative Hb levels ≤11.0. Currently it is not standard of care at the Cleveland Clinic to send all patients with Hb ≤11.0 due to secondary anemia to blood management. It is done currently at the provider/surgeons preference alone and not through a research protocol or guidelines. At the initial consultation visit a CBC will be drawn, patients will be given a consent form for the study and asked to review it. If a Hb ≤11.0 within 30 days of consultation visit is documented in EPIC, they will be consented and randomized at the consultation visit. All patients after initial consultation visit will be immediately sent to the lab for blood draw if they have not had Hb drawn within 30 days. Lab draw includes: CBC + differential, iron studies: iron, TIBC, ferritin, optional B12. If the initial consult visit occurs at Fairview or Hillcrest Hospital, the patient's follow up preoperative visit will be scheduled at the main campus where consent will be obtained. The blood management team then will receive the referral from primary surgeon's office via EPIC inbasket. Blood management coordinator will assess patient, arrange treatment, and orders will be cosigned by surgeon/referring provider. Blood management may further assess for symptoms of PICA, restless legs, and cold intolerance as symptomatic indicators of anemia. The Rand 36 study will be administered at either the consultation or the pre-operative visit. The PATSAT 35 will be administered at the postoperative visit only. Postoperative Hb levels will be collected by a CBC at the post-operative visit. All postoperative visits will be scheduled at the main campus. All surveys and consents will be obtained at visits that occur at the main campus.

[figure not shown]

Table 2: Blood Management Preoperative Iron Deficiency Algorithm

Blood loss intraoperatively will be measured as accurately as possible with suction device recording and quantitative blood loss and tapes/packs by weighing instead of only visual assessment.

[figure not shown]

Image: 1.0 -- Patient Flow Sheet

Justification for Sample Size:

Power Calculation:

Sample size was calculated to have 80% power to detect a difference between groups using a T-test at a significance level of 0.05. We assume that patients at 4 weeks will have a standard deviation in hemoglobin values of 1.2 g/dL (8) to detect a 1 g/dL difference between groups, we

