will need 48 patients total (24 per group) if the groups are of equal size. Assuming a 20% dropout rate, 60 patients total (30 per group) will be the target enrollment.

Cost and Payments to Subjects

The patients will have no additional costs due to participating in the study beyond the usual insurance copays and standard costs for appointments.

Quality Control Procedure:

Information will be provided to all department members involved in administration of the study. Follow up, data entry, and patient follow up will be closely followed by the research team (resident, fellow, staff physicians, MIGS NP's, Lead research nurse)

Process of Consent

Patients would be consented for participation in the study at their primary surgeon's office when shared decision making for proceeding with surgery is performed. Patients will receive no difference in care based on their participation in the study apart from the study protocol

Risks and Discomfort of the Project

The study has been designed to minimize as much risk as possible, and participants will be subjected to no more than minimal or standard risk for undergoing the intervention. Breach of confidentiality is a small risk. Physical risk are rare and unanticipated but would be limited to transfusion reaction to the IV iron therapy. There are no psychological risks for patients who participate in this study. Participants can also benefit from their participation in this study due to their altruistic motivation for partaking in research study they have contributed to scientific advancement.

Analysis plan

Approximately normally-distributed continuous measures will be summarized using means and standard deviations and will be compared using two-sample t-tests. Continuous measures that show departure from normality and ordinal measures will be summarized using medians and quartiles and will be compared using Wilcoxon rank sum tests. Categorical factors will be summarized using frequencies and percentages and will be compared using Pearson's chi-square tests or Fisher's Exact tests. All analyses will be done using SAS (version 9.4, The SAS Institute, Cary, NC) and a p < 0.05 will be considered statistically significant.

Timetable:

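### The primary hemoglobin comparison has no fixed analysis: the test depends on an undefined normality judgement, and neither option uses the care-provider strata or the enrolment hemoglobin

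*Combined protocol and SAP*

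**What the plan says.** Under Specific Aims/Objective, "The primary objective of this study is to compare the change in baseline hemoglobin levels in patients in the study" and control groups. The outcome is defined there: "Change in baseline hemoglobin levels is defined as the difference of the hemoglobin level obtained within 72 hours prior to surgery" and the level four weeks after it. This is a continuous measure.

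Under Justification for Sample Size, "Sample size was calculated to have 80% power to detect a difference between groups using a T-test at a significance level of 0.05". The inputs are a "standard deviation in hemoglobin values of 1.2 g/dL" at four weeks and a sample large enough "to detect a 1 g/dL difference between groups".

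The Analysis plan does not separate the primary outcome from the rest. Approximately normal continuous measures get means, SDs and a two-sample t-test. For the others: "Continuous measures that show departure from normality and ordinal measures will be summarized using medians and quartiles and will be compared using Wilcoxon". The paragraph names no normality test, threshold or plot. It does not say whether the change or each time point is checked, and it names no effect estimate or confidence interval.

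Methods and Study Design stratifies the permuted-block randomization (block size 2) by care provider and lists four surgeons. It requires a hemoglobin of 11 g/dL or lower within 30 days of the initial consultation, so every randomized patient has a hemoglobin value that precedes allocation.

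**The concern.** Three things are left open for the one comparison the trial is sized to make.

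- **The test is not fixed.** Whether the primary p-value comes from a t-test or a rank test depends on the observed data and on a judgement with no stated rule. Nobody could later show that either choice departed from the plan.
- **The target quantity is not fixed.** The sample size concerns a difference in g/dL tested on means. The Wilcoxon branch gives medians, quartiles and a rank p-value. Unless the arms differ only by a shift, that test does not address the mean difference. Different shapes are plausible, because treatment after referral may be observation, oral iron or intravenous iron.
- **Design information is unused.** Stratifying by provider balances providers across arms. An analysis that ignores the strata leaves between-provider variation in its error term, so its standard error is too large whenever providers differ. The enrolment hemoglobin, already collected, could also reduce residual variation.

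**Working it through.** **1. The plan's own figure.** Inputs from Justification for Sample Size: difference 1 g/dL, SD 1.2, alpha 0.05, power 80%. Sidedness is not stated; two-sided is assumed. The exact noncentral t calculation gives power 0.789 at 23 per group and 0.807 at 24, so 24 per group reproduces. One-sided testing would need 18 per group (normal approximation), which does not match. Dropout: 24/(1 − 0.20) = 30 per group, 60 in total. The stated N is right for a t-test.

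**2. What the normality rule does.** The plan gives no criterion, so Shapiro-Wilk at 0.05 on pooled residuals is assumed. There were 24 patients per arm and 20,000 simulated trials per row (Monte Carlo standard error about 0.15 points for a 5% rate).

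| Data, both arms | Type I error, rule | Power at 1 g/dL, rule | Power at 1 g/dL, fixed t-test |
|---|---|---|---|
| Normal | 5.1% | 81.2% | 81.1% |
| Skewed (gamma, shape 2) | 5.3% | 89.3% | 80.5% |
| Heavy tails (t, 4 df) | 5.3% | 88.6% | 82.0% |

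Repeat runs for normal and gamma data gave 4.9 to 5.4%. With equal means but different shapes (gamma against normal), the rule rejected in 6.3% of trials and the t-test in 5.2%. This shows that the rank test is not testing the mean difference. The two tests gave different significance verdicts in about 5 to 10% of trials with a true 1 g/dL shift.

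**3. Ignoring the provider strata.** Assume four providers with 6 patients per arm each, within-provider SD 1.2 and between-provider SD 0.5 (the documents give neither component).

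- True standard error of the difference: √(2 × 1.44/24) = 0.346, because provider effects cancel.
- Variance the unadjusted t-test sees, per arm: 1.44 + (6 × 3 × 0.25)/23 = 1.636. Its standard error: √(2 × 1.636/24) = 0.369.
- Ratio: 0.346/0.369 = 0.938. The effective critical value is 2.013/0.938 = 2.146, a two-sided level of about 3.7%.

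Simulation (40,000 trials) agrees: 3.7% unadjusted against 4.9% with provider in the model, and power at 1 g/dL of 76.8% against 80.5%. If 1.2 is instead the total SD, power is 83.9% against 87.6%. A separate run at the same between-provider SD gave 3.5%. At a between-provider SD of 0.25 the unadjusted level is 4.5 to 4.7%; at 0 there is nothing to gain.

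**4. Adding enrolment hemoglobin.** The model has six parameters (intercept, arm, three for provider, one for hemoglobin), leaving 48 − 6 = 42 degrees of freedom against 46 for the t-test. If the added terms explain nothing, power is 80.5% instead of 80.7%. If enrolment hemoglobin correlates r with the outcome, the residual SD is 1.2 × √(1 − r²):

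| r (assumed) | Residual SD | Power at 1 g/dL |
|---|---|---|
| 0.2 | 1.176 | 82.1% |
| 0.3 | 1.145 | 84.0% |
| 0.5 | 1.039 | 90.3% |

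**5. Which hemoglobin value can be the covariate.** The value within 72 hours before surgery comes after randomization and preoperative treatment. Suppose treatment raises both that value and the four-week value by 1 g/dL, with equal SDs and pre-post correlation ρ. Adjusting for the 72-hour value gives a treatment coefficient of 1 − ρ: 0.7, 0.5 and 0.3 at ρ = 0.3, 0.5 and 0.7. That is neither the 1 g/dL difference in four-week values nor the zero difference in change. The enrolment value does not have this problem.

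**The case against.** The strongest case for leaving the plan alone has four parts.

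- **The t-test is already indicated.** The power section names it, and the Analysis plan makes it the rule for approximately normal data. This stands as a reading of intent. However, the power section states the basis for N, and the paragraph that governs analysis does not carry the t-test over as the primary analysis.
- **The harm to error rates is negligible.** This stands. A reader might infer that the rule lets the analyst take the smaller of two p-values, which in simulation gives 5.8 to 6.6%. The documents do not support that: the choice is tied to distribution, not significance, so those figures describe breaking the plan. Nor do they state that the analyst is unblinded. No blinding is described, but the outcome is a laboratory value.
- **Fixing a mean-based test is not free.** This also stands. Under a skewed pure shift, a fixed t-test has 80.5% power against 89.3% for the rule.
- **The t-test branch promises no difference or interval either, and medians are in g/dL.** Correct. The missing effect estimate is a gap in both branches, and under a pure location shift Wilcoxon does test that shift. The plan gives no ground for assuming a pure shift.

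**Conclusion.** The point holds as one of specification and precision; it is a minor improvement. The primary outcome has no fixed test or effect estimate, and the analysis ignores the stratification factor and a usable pre-randomization covariate. The rule leaves type I error at about 5.1 to 5.4% when the arms share a shape. It would be wrong to conclude that it inflates false positives materially or that the sample size is in error: 24 per group reproduces.

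The gain from adjustment depends on assumptions. At a between-provider SD of 0.5 g/dL, the unadjusted level of 3.5 to 3.7% returns to about 5% and power rises by just under 4 points. The hemoglobin covariate adds more only if it predicts the outcome. Because eligibility caps hemoglobin at 11 g/dL, its range is restricted and the correlation may be low. All power figures take 1.2 g/dL as the SD of the analysed outcome, as the plan does, although it is stated for four-week values and the outcome is a change.

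**What to change.** Add to the Analysis plan: the primary hemoglobin outcome is analysed by one linear model with terms for treatment arm, care provider and enrolment (pre-randomization) hemoglobin. The adjusted between-group difference in g/dL is reported with a 95% CI whatever the normality check shows. State that the hemoglobin taken within 72 hours before surgery is not a covariate. Name the Wilcoxon test as a sensitivity analysis and keep the normality rule for descriptive summaries.

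The cost is a few sentences. No new data or visits are needed, and enrolment stays at 60. The price is four degrees of freedom relative to the t-test (about 0.2 points of power if the covariates explain nothing) and the possible loss of the rank test's power advantage if the data are strongly skewed.
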